3. SPECIFIC AIMS

3.1 Overall Study Design and Plan

The study uses a double-blinded, placebo lead-in, randomized, parallel group, PBO-controlled design. For this clinical trial, one-hundred individuals over 17 years of age meeting operationalized criteria for Long-COVID will be recruited. These 100 participants will undergo a placebo lead-in period of two weeks. Sixty participants will then be randomized to NR (TruNiagen®, Chromadex) 1000 mg twice daily for 22 weeks, and 40 will receive placebo for the next 10 weeks followed by NR for 10 weeks. Outcomes will consist of standardized cognitive, neuropsychiatric, physical, functional and biomarker assessments as well as daily sleep and activity monitoring with wearable actigraphy.

Randomized, Placebo-Controlled Parallel Group Clinical Trial of Nicotinamide Riboside to evaluate NAD+ Levels in Individuals with Persistent Cognitive and Physical Symptoms After COVID19 Illness ("Long-COVID")

Version 1.1

The study will also help better understand the nature of long-COVID by comparing this group with a healthy control group of individuals who were infected with COVID-19 but fully recovered. To better address this aim, we will also increase our sample size of individuals with long-COVID by testing individuals with long-COVID ages 18 and older who will only complete 1 visit. Comparing these groups will help establish differences in NAD+ levels at baseline associated with long-COVID, as well as help elucidate the cognitive profile, neuropsychiatric and physical functioning, and markers of glia and neural functioning in this population. Participants in these additional cohorts will only complete one visit and will not be administered NR or PBO.

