4.1.2 Exclusion Criteria

A subject will not be eligible for participation in the **clinical trial** if they meet any of the following criteria:

- 1. Any specific CNS disease history, such as major clinical stroke, brain tumor, normal pressure hydrocephalus, multiple sclerosis, delirium, significant head trauma with persistent neurological of cognitive deficits or complaints;
- 2. Clinically significant unstable medical condition that could affect safety or compliance with the study and would, in the opinion of the investigator, pose a risk to the participant if they were to participate in the study;
- 3. Was intubated due to COVID-19;
- 4. History of neuroimaging with evidence of major infarction, injury, infection, or other focal lesions that may be related to cognitive dysfunction;
- 5. Major active or chronic unstable psychiatric illness (e.g. depression, bipolar disorder, obsessive compulsive disorder, schizophrenia) within the previous year;
- 6. Current suicidal ideation;
- 7. History of alcohol or other substance abuse or dependence within the past two years;
- 8. Any significant systemic illness or medical condition that could affect safety or compliance with study;
- 9. Laboratory abnormalities in Vitamin B12, Thyroid Stimulating Hormone (TSH), or other common laboratory parameters that might contribute to cognitive dysfunction or other abnormalities in hematological, hepatic or renal function tests;

Randomized, Placebo-Controlled Parallel Group Clinical Trial of Nicotinamide Riboside to evaluate NAD+ Levels in Individuals with Persistent Cognitive and Physical Symptoms After COVID19 Illness ("Long-COVID")

Version 1.1

- 10. Current use of medications with psychoactive properties that in the opinion of the principal investigator, may be deleteriously affecting cognition (e.g., anticholinergics, antihistamines, antipsychotics, sedative hypnotics, anxiolytics);
- 11. Any known hypersensitivity to nicotinamide riboside, or its principal metabolite, nicotinamide mononucleotide;
- 12. No consumption of dietary supplements containing more than 100mg of niacin, nicotinamide riboside (NR), or nicotinamide mononucleotide (NMN) as the primary agents 30 days prior to baseline and for the duration of the trial.
- 13. Use of other investigational agents or interventions one month prior to entry and for the duration of the trial;

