5.4 Reasons for Withdrawal

A study subject will be discontinued from participation in the study if:

- Any clinical adverse event (AE), concurrent illness, or other medical condition or situation occurs such that continued participation in the study would not be in the best interest of the subject.
- The subject meets any exclusion criteria (either newly developed or not previously recognized).
- Tests positive for SARS-CoV-2 PCR or COVID-19 Antigen Rapid Self-Test
- The subject is less than 80% or greater than 120% compliant with NR dosing.

Subjects are free to withdraw from participation in the study at any time upon request.

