6. STUDY PROCEURES

6.1 Schedule of Assessments for the clinical trial

	Week 0	Week 2	Week 7	Week 12	Week 17	Week 22		Week 24
Activity (n=100)	Screening/Lead- In	Baseline	Visit 1	Visit 2	Visit 3	Visit 4	Early DC	Phone Follow Up
Informed Consent ¹	X							
Demographics	X							
Medical & COVID-19 History/ Safety Labs ^{2,3}	X							
Long COVID-19 symptoms assessment	X	X	X	X	X	X	X	X
SARS-CoV-2 PCR test	X							
Height and Weight	X			X		X	X	
Vital Signs	X	X	X	X	X	X	X	
Inclusion/ Exclusion Review ⁴	X	X	X	X	X	X		
Physical and Neurological Examination ⁵	X			X		X	X	
MMSE	X			X		X	X	
Concomitant Medications and Supplements ⁴	X	X	X	X	X	X	X	X
Randomization	X							

Randomized, Placebo-Controlled Parallel Group Clinical Trial of Nicotinamide Riboside to evaluate NAD+ Levels in Individuals with Persistent Cognitive and Physical Symptoms After COVID19 Illness ("Long-COVID") Version 1.1

Dispense NR/PBO ⁴	X	X	X	X	X			
Accountability and Compliance		X	X	X	X	X	X	
AE Reporting ^{4,6}		X	X	X	X	X	X	X
Office Cognitive Assessment ⁷		X		X		X	X	
Neuropsychiatric Assessment ⁸	X	X	X	X	X	X	X	
Office Functional Assessment		X		X		X	X	
Blood Collection for PK and Biomarkers ⁹		X	X	X	X	X	X	
Subjective cognitive concerns assessment ¹⁰	X	X	X	X	X	X	X	
Physical activity Assessment ¹¹	X	X	X	X	X	X	X	
Sleep Assessment ¹²	X	X	X	X	X	X	X	
Daily Activity Assessment ¹²			ongo	ing		ongoingX		

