6.2.3 Follow Up Visits (Weeks 7, 12 and 17)

These visits will take place every 5 weeks (± 2 days) following Baseline.

Randomized, Placebo-Controlled Parallel Group Clinical Trial of Nicotinamide Riboside to evaluate NAD+ Levels in Individuals with Persistent Cognitive and Physical Symptoms After COVID19 Illness ("Long-COVID")
Version 1.1

¹These procedures can take place virtually via Zoom videoconference if necessary.

- Review and document concomitant medications, supplements, and therapies¹
- Assess COVID-19 related symptoms
- Perform physical assessments
- Perform physical and neurological examination
- Measure vital signs
- Dispense study supplement or PBO¹
- Assess study supplement compliance
- Administer battery of cognitive assessments (only week 12)
- Administer questionnaires about neuropsychiatric symptoms, sleep, physical activity and others
- Blood draw and a collect dried blood spot sample for biomarker analysis
- Assess and document adverse events (AEs) and changes to medical history¹

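### Section 5.4 ends study follow-up on any positive SARS-CoV-2 test, so a removal between Weeks 2 and 12 forfeits the only scheduled placebo-controlled RBANS and TMT-B

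*Combined protocol and SAP*

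**What the plan says.** Section 5.4 (Reasons for Withdrawal) gives a list of events, each of which ends the person's participation in the study and not merely the use of product. One bullet reads "Tests positive for SARS-CoV-2 PCR or COVID-19 Antigen Rapid Self-Test". It is not limited by date, symptoms or investigator judgement. The first bullet of the same list, by contrast, applies only when continuing would be against the participant's interest.

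In the section 6.1 schedule, the row "SARS-CoV-2 PCR test" is marked at Week 0 only, and no later visit list in section 6.2 contains a test. The row "Office Cognitive Assessment" is marked at Weeks 2, 12 and 22 and at early discontinuation. Sections 6.2.3 and 7.1.2.2.2 agree that the battery is not given at Weeks 7 or 17. Under section 3.1, "40 will receive placebo for the next 10 weeks followed by NR for 10 weeks".

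Section 6.2.5 invites people who leave early to an exit visit within 7 days of stopping treatment, and that visit includes cognitive testing. Section 5.4.1 describes the exit visit only for withdrawal of consent. Section 9.1 commits to intention-to-treat for all outcomes with a repeated-measures mixed model. RBANS, TMT-B, ECog and NAD+ are its lead outcomes. Section 9 does not say which time point an exit assessment belongs to, or how withdrawal or reinfection is handled.

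**The concern.** The rule stops data collection because of something that happens after randomisation and that the trial does not look for systematically. Of two participants with the same reinfection, the one who takes a test leaves and the one who does not stays. For RBANS and TMT-B, everything the placebo comparison can use is collected at a single scheduled visit, so a removal before Week 12 takes away that participant's whole scheduled contribution to it.

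An intention-to-treat analysis needs outcomes after such events. Scores that were collected can be set aside later if reinfection is thought to distort them; scores that were never collected cannot be recovered. The mixed model does not solve this. It relies on a missing-at-random assumption, and a participant with no post-baseline RBANS or TMT-B adds no change score for those outcomes. The pooled analysis in 9.1.2, which expects everyone to reach 10 weeks of NR, is also affected.

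**Working it through.** **What is lost, by outcome**

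- RBANS and TMT-B: scheduled at Weeks 2, 12 and 22. By Week 22 both arms are on NR, so Week 12 is the only scheduled placebo-controlled post-baseline value. Removal between Weeks 2 and 12 loses it.
- ECog, NAD+, BAI, BDI and PSQI: also collected at Week 7. Someone removed after Week 7 keeps one placebo-controlled value, so the loss is partial.
- Exit battery: by invitation, within 7 days of stopping treatment, and so probably close to the acute infection. Section 9 gives it no time point.

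**How many people**

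The documents give no reinfection or dropout rate and no sample-size calculation, so there is no stated figure to reproduce. Assume that 5-20% test positive over Weeks 2-22 at a constant rate. That is 0.25 to 1 person per week per 100 over 20 weeks.

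- Removed before Week 12: 10 × 0.25 to 10 × 1 = 2.5-10 of 100.
- Removed before Week 22: 20 × 0.25 to 20 × 1 = 5-20 of 100.
- Lacking the 10-week NR value pooled in 9.1.2: NR-NR arm 60 × 2.5% to 60 × 10% = 1.5-6; PBO-NR arm 40 × 5% to 40 × 20% = 2-8; total 3.5-14 of 100.

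**Power at Week 12**

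Assume a two-sample comparison, two-sided alpha 0.05, equal removal in both arms and no Week 12 value from anyone removed. Power uses the noncentral t distribution with a difference of 0.578 SD, chosen because it gives about 80% power at full numbers. The detectable difference at 80% power uses the normal approximation (1.960 + 0.842) × √(1/n₁ + 1/n₂).

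| Removed before Week 12 | NR v placebo | Power at 0.578 SD | Detectable difference |
|---|---|---|---|
| 0% | 60 v 40 | 80.1% | 0.572 SD |
| 2.5% | 58.5 v 39 | 79.0% | 0.579 SD |
| 5% | 57 v 38 | 78.0% | 0.587 SD |
| 10% | 54 v 36 | 75.7% | 0.603 SD |

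**Power if the infected are kept**

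Let 10% in each arm be infected and kept, with reinfection shifting the score by c SD. The outcome SD becomes √(1 + 0.1 × 0.9 × c²), which is 1.011 for c = 0.5 and 1.044 for c = 1.

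- Treatment effect unchanged in the infected: power 79.2% (c = 0.5) or 76.6% (c = 1).
- Half the effect lost in the infected, so the mean difference is 0.95 × 0.578 = 0.549 SD: power 75.0% or 72.3%.

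The removal rule gives 75.7% at the same 10%. Keeping people may therefore give slightly more or slightly less power.

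**Bias**

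To first order, bias = (removal rate on placebo − removal rate on NR) × reinfection effect. It is zero if removal is equal by arm and the treatment effect is the same in infected participants. With 10% v 5% removed and a 0.5 SD reinfection effect, it is 0.05 × 0.5 = 0.025 SD. The direction cannot be told from the documents.

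**The case against.** **The bullet may be meant for screening.** Under 6.2.1.1 anyone who signs consent counts as enrolled, and 6.2.1 dispenses lead-in placebo at the visit where the PCR is taken, so a positive Week 0 result needs a removal rule. The mention of a rapid self-test also matches the entry tests of the one-time-visit cohorts. No section describes self-testing after baseline. This is a fair account of where the bullet may have come from, but as written it has no end date. If screening was the intent, the fix only states it.

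**Other text is softer.** Section 8.4.1 implies that a person can stop product and stay in the study. Section 11.3.1 leaves removal to the investigators, and its four criteria do not include a positive test. Neither overrides the mandatory wording of 5.4.

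**Retained scores will be contaminated, and the remedy also depends on testing.** Both are true. Some scores will reflect reinfection, rescheduling and the sensitivity analysis still apply only to those who test, and the 9.1.2 covariate for time since acute infection becomes ambiguous after a second infection. But the primary analysis would then no longer lose outcomes because of a test.

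**Stronger readings that a reader might infer.**

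- That the rule seriously weakens the trial or biases its result. The documents supply no rate, and the assumed range gives small effects. Blinding makes a large difference between arms unlikely.
- That keeping people restores power. The figures above show that it need not.
- That every outcome is lost. Week 7 values exist for several.
- That the compliance bullet, "The subject is less than 80% or greater than 120% compliant with NR dosing", would remove the same person anyway once dosing is suspended for illness. The documents do not establish this: section 8.5 calls for re-education first and leaves persistent non-compliance to the PI. No section fixes the interval over which compliance is judged or says that investigator-suspended doses count.

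**Conclusion.** The point holds as a low-cost improvement. Followed literally, 5.4 ends primary-outcome follow-up on a post-randomisation event that is detected haphazardly, while 9.1 promises intention-to-treat. No reason for the rule is given, and the best-interest bullet in 5.4 already covers participants who would be harmed by continuing.

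The size is unknown and probably modest. Under the assumed 5-20% infection rate, 2.5-10 of 100 participants lose the Week 12 RBANS and TMT-B, power drops by about 1 to 4 percentage points, and bias is zero or a few hundredths of an SD. These figures rest on the assumed rate, alpha, effect size and reinfection effect, none of which is in the documents. What the change gains is complete follow-up of the randomised groups and freedom from selection by testing.

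**What to change.** - **Section 5.4.** Limit the bullet to a positive PCR or rapid antigen test at or before the Week 2 baseline visit. Add that a later positive test is not by itself a ground for withdrawal from the study. Product may still be suspended under 8.4, and the best-interest bullet still applies.
- **Follow-up.** Record a later positive test as a dated adverse event through the existing question, and keep the participant in all remaining visits. If an in-person battery falls during acute infection, reschedule it and supply product meanwhile under 6.2.9 unless it is suspended.
- **Section 9.1.** Include these participants in the intention-to-treat mixed model. Add a sensitivity analysis that sets scores after the first positive test to missing.

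The cost is wording in 5.4, an exception to the visit windows (±2 days in 6.2.3, 3 days in 6.2.9) and two sentences in 9.1; no new case report form item is needed. The price is that some retained scores reflect reinfection and a few visits fall outside the window.

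The sponsor can settle the details: how long to defer, whether placebo participants wait for the rescheduled Week 12 battery before starting NR, and how suspended days count towards compliance. For scale, under the same assumed rate, a 4-week interval defers 4 × 0.25 to 4 × 1 = 1-4 of 100 at each battery and needs at most 8 capsules × 28 days = 224 capsules per deferral. An 8-week interval, closer to the 2 months since infection required at entry, would defer 2-8 of 100.

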5.4.1 Handling of Withdrawals

A subject may choose to discontinue participation in the study at any time. An Early Termination visit will occur when a subject withdraws consent, i.e. withdrawing his or her participation in future study procedures.

5.5 Termination of Study

This study may be prematurely terminated if, in the opinion of the investigator, there is sufficient reasonable cause.

Circumstances that may warrant termination include, but are not limited to:

- Determination of unexpected, significant, or unacceptable risk to subjects.
- Unsatisfactory enrollment.
- Insufficient adherence to protocol requirements.
- Data that are not sufficiently complete and/or evaluable.

Randomized, Placebo-Controlled Parallel Group Clinical Trial of Nicotinamide Riboside to evaluate NAD+ Levels in Individuals with Persistent Cognitive and Physical Symptoms After COVID19 Illness ("Long-COVID")

Version 1.1

If the study is prematurely terminated or suspended, the investigators will promptly inform the institution are regulatory authorities of the termination or suspension and the reason(s) for the termination or suspension. IRB/IEC will also be informed promptly and provided the reason(s) for the termination or suspension by the investigator, as specified by applicable regulatory requirement(s).				
Randomized, Placebo-Controlled Parallel Group Clinical Trial of Nicotinamide Riboside to evaluate NAD+ Levels in Individuals with Persistent Cognitive and				

6. STUDY PROCEURES

6.1 Schedule of Assessments for the clinical trial

	Week 0	Week 2	Week 7	Week 12	Week 17	Week 22		Week 24
Activity (n=100)	Screening/Lead- In	Baseline	Visit 1	Visit 2	Visit 3	Visit 4	Early DC	Phone Follow Up
Informed Consent ¹	X							
Demographics	X							
Medical & COVID-19 History/ Safety Labs ^{2,3}	X							
Long COVID-19 symptoms assessment	X	X	X	X	X	X	X	X
SARS-CoV-2 PCR test	X							
Height and Weight	X			X		X	X	
Vital Signs	X	X	X	X	X	X	X	
Inclusion/ Exclusion Review ⁴	X	X	X	X	X	X		
Physical and Neurological Examination ⁵	X			X		X	X	
MMSE	X			X		X	X	
Concomitant Medications and Supplements ⁴	X	X	X	X	X	X	X	X
Randomization	X							

Randomized, Placebo-Controlled Parallel Group Clinical Trial of Nicotinamide Riboside to evaluate NAD+ Levels in Individuals with Persistent Cognitive and Physical Symptoms After COVID19 Illness ("Long-COVID") Version 1.1

Dispense NR/PBO ⁴	X	X	X	X	X			
Accountability and Compliance		X	X	X	X	X	X	
AE Reporting ^{4,6}		X	X	X	X	X	X	X
Office Cognitive Assessment ⁷		X		X		X	X	
Neuropsychiatric Assessment ⁸	X	X	X	X	X	X	X	
Office Functional Assessment		X		X		X	X	
Blood Collection for PK and Biomarkers ⁹		X	X	X	X	X	X	
Subjective cognitive concerns assessment ¹⁰	X	X	X	X	X	X	X	
Physical activity Assessment ¹¹	X	X	X	X	X	X	X	
Sleep Assessment ¹²	X	X	X	X	X	X	X	
Daily Activity Assessment ¹²			ongo	ing		ongoingX		

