3.2.1 Standardized Cognitive, Functional, and Neuropsychiatric Outcome Measures

The primary outcome of this study will be objective measures of cognitive performance and subjective cognitive concerns measured with the following tests:

O The Mini-Mental State Examination (MMSE)²², Wechsler Adult Intelligence Scale-Fourth Edition (WAIS-IV) Digit Span backwards²³, Repeatable Battery for the Assessment of Neuropsychological Status (RBANS)²⁴, the Trail Making Test (TMT)²⁵, the Delis-Kaplan Executive Function System (DKEFS) Verbal Fluency²⁶, and the Continuous Performance Test (CPT). ²⁷ Subjective ratings of everyday cognitive functioning will be measured using items from the Behavior Rating Inventory of Executive Function (BRIEF-A)²⁸ at week 2, week 12 and week 22, and the Everyday Cognition scale (ECog)²⁹ will be measured at each visit.

The secondary and tertiary clinical and exploratory biomarker outcomes of this study will be:

• Assessment of neuropsychiatric symptoms as measured by:

Randomized, Placebo-Controlled Parallel Group Clinical Trial of Nicotinamide Riboside to evaluate NAD+ Levels in Individuals with Persistent Cognitive and Physical Symptoms After COVID19 Illness ("Long-COVID")

Version 1.1

- o Ratings of mood and anxiety will be measured using the Post Traumatic Stress Disorder Checklist-Civilian (PCL-C)³⁰, Beck Anxiety Inventory (BAI)³¹ and Beck Depression Inventory (BDI)³². These standard measures will be administered at each visit.
- Assessment of physical functioning as measured by:
 - o The Fatigue Severity Scale³³.
 - Objective daily physical activity levels and sleep data collected using wrist actigraphy (Fitbit Charge 4).
 - Subjective sleep ratings (Pittsburgh Sleep Quality Index)³⁴ and physical activity (International Physical Activity Questionnaire [IPAQ])³⁵ measures will be collected using questionnaires at each visit.
- Safety and tolerability will be assessed with adverse event (AE) reporting conducted at every visit.
- Plasma for biomarkers will be collected at Week 2, and at every 5 weeks until the end-of-study, and at the one-time visit for HC and long-covid participants. Plasma biomarkers assays will consist of ultrasensitive immunochemical measures of proteins reflecting neurodegeneration/neural injury (e.g. NfL, IL-6 and GFAP), as well as NAD+/NADH).
- Cerebral neurophysiology will be measured with functional MRI (optional sub-study).

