6.2.1 Screening/Lead-In Visit (Week 0)

The screening procedures will determine the subject's eligibility for the study and will take approximately 3 hours.

The following procedures will take place at the Screening/Lead-In visit:

- Obtain written informed consent from the subject.
- Obtain demographics and medical history, including assessment of COVID-19 symptoms
- Complete SARS-CoV-2 PCR test
- Safety Labs
- Perform physical and neurological examination
- Measure Vital Signs
- Measure height and weight
- Review and document concomitant medications, supplements, and therapies
- Administer the MMSE
- Provide Fitbit
- Administer questionnaires about neuropsychiatric symptoms, sleep, physical activity, and others.
- Dispense PBO

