6.2.2 Baseline Visit (Week 2)

The following procedures will be performed and will take approximately 4-5 hours depending on participation in the MRI sub-study. If the subject has elected to participate in the MRI sub-study, the visit may occur over multiple days as long as all tasks are completed during the study visit window.

- Measure Vital Signs
- Blood draw and a collect dried blood spot sample for biomarker analysis
- Assess study supplement compliance
- Assess COVID-19 related symptoms
- Administer cognitive assessments
- Administer questionnaires about neuropsychiatric symptoms, sleep, physical activity and others
- Assess and document AEs and changes to medical history¹
- Review and document concomitant medications, supplements, and therapies¹
- Dispense study supplement or PBO¹
- Perform optional MRI scan
- Reassess inclusion and exclusion criteria¹

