9.1 Primary analysis

For all outcomes, we will perform intention-to-treat (ITT) analysis and mixed-effects model repeated measures (MMRM). Group (NR-NR vs. PBO-NR sequence), time, and group by time interactions will be included in the MMRM as fixed effects. The study's outcomes will be the change score of ECog, RBANS, and TMT-B from baseline, and the change in NAD+ levels from baseline. We also will examine changes in the FSS, BAI, BDI, and PSQI scores. An unstructured covariance matrix will be used to account for the correlation of repeated measures within a participant. Age, sex, and education will be included in the models as covariates.

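### ECog, BAI, BDI and PSQI are scored twice before any NR, but the section 9.1 model adjusts for neither score: an optional gain in precision is left unused

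*Combined protocol and SAP*

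**What the plan says.** **Collection.** The table in section 6.1 marks the row "Subjective cognitive concerns assessment", and the neuropsychiatric and sleep rows, at Week 0 and again at Week 2. Section 3.2.1 agrees: ECog "will be measured at each visit"; of PCL-C, BAI and BDI it says "These standard measures will be administered at each visit"; the PSQI and IPAQ "measures will be collected using questionnaires at each visit". The Week 0 visit list in section 6.2.1 includes "Administer questionnaires about neuropsychiatric symptoms, sleep, physical activity, and others".

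**Timing relative to NR.** Section 3.1 states "These 100 participants will undergo a placebo lead-in period of two weeks", and section 6.2.1 dispenses placebo at Week 0. Both scores therefore precede NR in both arms.

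**Analysis.** Section 6.2.2 labels the Week 2 visit as baseline. Section 9.1 specifies an MMRM on change from baseline for ECog, RBANS, TMT-B and NAD+, and also examines changes in FSS, BAI, BDI and PSQI. Beside group, time and their interaction, "Age, sex, and education will be included in the models as covariates". No part of section 9 gives the Week 0 scores a role or enters the Week 2 score as a covariate.

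**The concern.** Self-report scores vary from one occasion to the next. A change score with no baseline covariate carries all the noise of the single reading that is subtracted. Two pre-treatment readings are scheduled for four of the scales in section 9.1, and neither is used to explain variation in the follow-up score.

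The stake is the width of the confidence interval for NR against placebo. It matters most for ECog, which belongs to the primary outcome in section 3.2.1 and is the first change score named in section 9.1. The trial has 100 participants, 40 of them on placebo first, and the body of the plan contains no power calculation, so precision that needs no new data is worth considering.

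**Working it through.** **No planned figure to reproduce.** The contents page lists a sample-size section, but the body gives no alpha, power, effect size, SD or within-person correlation. All correlations below are assumed.

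**Which outcomes qualify.** An outcome must be modelled in section 9.1 and scheduled at both Week 0 and Week 2.
- ECog, BAI, BDI and PSQI meet both conditions.
- PCL-C and IPAQ are collected twice but appear in no model named in section 9.1.
- RBANS, TMT-B and NAD+ have no Week 0 value in the table.
- FSS is modelled, but the text gives it no visit timing, so it is left out.

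The footnotes of the section 6.1 table are not in the text available to me. I matched instruments to rows from section 3.2.1 and the section 6.2 footnotes.

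**Formulas.** Take SD 1 at each visit and one follow-up visit. Let a = corr(Week 0, Week 2), b = corr(Week 2, follow-up), c = corr(Week 0, follow-up).
- Planned change from Week 2: variance 2 - 2b
- Week 2 as covariate: 1 - b²
- Week 0 and Week 2 as covariates: 1 - b² - (c - ab)²/(1 - a²)
- Change from the mean of the two scores: 1 + (1 + a)/2 - (b + c)

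Worked case a/b/c = 0.75/0.60/0.55: change 2 - 1.20 = 0.80; Week 2 covariate 1 - 0.36 = 0.64; both 0.64 - (0.55 - 0.45)²/0.4375 = 0.617. Week 0 adds 1 - 0.617/0.64 = 3.6%.

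| a / b / c (assumed) | Change | Week 2 cov. | Both cov. | Week 0 adds | Both vs change |
|---|---|---|---|---|---|
| 0.5 / 0.5 / 0.5 | 1.000 | 0.750 | 0.667 | 11% | 33% |
| 0.6 / 0.6 / 0.6 | 0.800 | 0.640 | 0.550 | 14% | 31% |
| 0.7 / 0.7 / 0.7 | 0.600 | 0.510 | 0.424 | 17% | 29% |
| 0.8 / 0.8 / 0.8 | 0.400 | 0.360 | 0.289 | 20% | 28% |
| 0.9 / 0.7 / 0.7 | 0.600 | 0.510 | 0.484 | 5% | 19% |
| 0.75 / 0.60 / 0.55 | 0.800 | 0.640 | 0.617 | 4% | 23% |
| 0.8 / 0.7 / 0.6 | 0.600 | 0.510 | 0.506 | 1% | 16% |
| 0.85 / 0.6 / 0.5 | 0.800 | 0.640 | 0.640 | 0% | 20% |
| AR(1), 0.95 per week | 0.803 | 0.642 | 0.642 | 0% | 20% |
| AR(1), 0.98 per week | 0.366 | 0.332 | 0.332 | 0% | 9% |

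The Week 0 term is a square, so apart from degrees of freedom it cannot raise the variance. It vanishes when c = ab, that is, when Week 0 predicts follow-up only through Week 2.

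**Detectable difference.** With 60:40 allocation, two-sided 0.05, 80% power and complete data (all but the allocation assumed), it is (1.960 + 0.842) × √(1/40 + 1/60) × √variance = 0.572 × √variance. At 0.7/0.7/0.7 this gives 0.443 SD (change), 0.408 (Week 2) and 0.372 (both). At 0.8/0.7/0.6 it gives 0.443, 0.408 and 0.407.

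**Averaging is not a safe substitute.** With equal correlations, averaging the two scores into the reference cuts change-score variance by 25%. At 0.90/0.70/0.63 it gives 1 + 0.95 - 1.33 = 0.62 against 0.60, about 3% worse. At 0.80/0.70/0.56 it gives 1 + 0.90 - 1.26 = 0.64 against 0.60, about 7% worse.

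**The case against.** The case against is substantial.

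- **It is a choice, not a mistake.** The end of a placebo lead-in is a coherent baseline, and Week 0 was measured before the lead-in, under a different condition. This stands. A reader might infer that the planned contrast is biased or invalid; nothing in the documents supports that.
- **The increment from Week 0 may be nil.** This stands. Equal correlation at all gaps is the favourable case. For PSQI, section 7.1.2.1.5 gives a one-month recall, so windows two weeks apart share about half their span and the second score adds less.
- **Most of the gain may come from Week 2.** In the table, Week 2 alone cuts the change-score variance by (1 - b)/2, which is 10-25% for b from 0.8 to 0.5. This also stands, and is why both covariates belong in one amendment.
- **The scope is narrow.** A reader might infer that all six questionnaires lose a second baseline in the model. PCL-C and IPAQ are in no named model, and three of the four lead outcomes in section 9.1 have no Week 0 score.
- **Week 0 scores are not useless to the study.** They come from the eligibility visit, and section 10.1.1 has BDI suicidality answers reviewed after completion. The gap is in the model only.
- **The fix has costs.** Entering both scores by visit over four follow-up visits means eight slopes per model, and a missing Week 0 score could drop a randomised participant. Both are manageable: a single Week 0 slope reduces the count to five, and imputation deals with missing scores.

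Section 6.1 marks randomisation at Week 0, while section 3.1 places it after the lead-in. Under either reading NR cannot have affected the two scores, so adjusting for both does not bias the comparison.

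**Conclusion.** The point holds as an optional precision improvement for ECog, BAI, BDI and PSQI. The Week 0 score adds about 0-20% variance reduction beyond Week 2 adjustment, with the value set by correlations that the documents do not give. Both covariates together cut the planned change-score variance by roughly 16-33% in most cases shown, and by as little as 9% under slow AR(1) decay.

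These figures assume equal variances, complete data and a slope free at the visit considered; a common Week 0 slope could gain slightly less.

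A flat claim that 25% of the variance is being wasted is not supported. That number belongs to averaging under equal correlations, not to covariate adjustment, and averaging can lose precision under decay.

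That Week 2 is the reference is itself an inference from the visit labels. Section 9.1 does not define baseline, and section 7.1.2.5 calls Week 0 baseline for the MRI.

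**What to change.** In section 9.1:
1. Define baseline as the Week 2 visit.
2. For ECog, BAI, BDI and PSQI, add the Week 2 score (by visit) and the Week 0 score as MMRM covariates. Do not average them into the change score.
3. Impute a missing Week 0 score from pre-treatment data without regard to arm, so that no randomised participant is dropped.

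This fix does not touch RBANS, TMT-B or NAD+, which have only a Week 2 value, or PCL-C and IPAQ, which have no named model.

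The cost is two or three sentences, no new data, and a few degrees of freedom: four Week 2 slopes and one Week 0 slope when all four follow-up visits are modelled. It should be written before the unblinding described in section 9.1.3, so that the covariates are not chosen with results in view.
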